9.4.2 Exclusion Criteria

Urology

1. Any prior invasive prostate intervention (e.g., “Radiofrequency” thermotherapy, balloon, microwave thermotherapy, “Prostatic Urethral Lift”, “Transurethral Resection”, or laser) or other surgical interventions of the prostate.
2. Undergone a prostate biopsy within 60 days prior to the scheduled treatment date or has an imminent need for surgery.
3. Verified acute bacterial prostatitis within last 12 months documented by culture.
4. Active or history of epididymitis within the past 3 months.
5. Urethral strictures, bladder neck contracture, unusual anatomy or muscle spasms that would prevent the introduction and use of the Rezūm device.
6. Diagnosed bladder, urethral or ureteral stones or active stone passage in the past 6 months, provided that stones that are known to be in the kidney and have been stable for a period exceeding 3 months are permissible.
7. Subject interested in maintaining fertility.
8. Use of the following medications where the dose is not stable (stable dose defined as the same medication and dose in the last three months):
 - a. Beta-blockers;
 - b. Anticonvulsants;
 - c. Antispasmodics;
 - d. Antihistamines;
 - e. Alpha blockers for BPH and anticholinergics or cholinergics;
 - f. Type II, 5-alpha reductase inhibitor (e.g., finasteride (Proscar, Propecia));
 - g. Dual 5-alpha reductase inhibitor (e.g., dutasteride (Avodart));
 - h. Estrogen, drug-producing androgen suppression, or anabolic steroids;
 - i. PD5 Inhibitors (e.g., Viagra, Levitra or Cialis)
9. Subjects who have had an incidence of spontaneous urinary retention either treated with indwelling transurethral catheter or suprapubic catheter 6 months prior to baseline. A provoked episode now resolved is still admissible.
10. Evidence of atonic neurogenic bladder evaluated by a baseline urodynamic assessment.
11. Visible hematuria with subject urine sample without a known contributing factor.
12. Presence of a penile implant or stent(s) in the urethra or prostate.
13. Active urinary tract infection by culture within 7 days of treatment or two documented independent urinary tract infections of any type in the past 6 months.

Gastroenterology

14. Previous pelvic irradiation or radical pelvic surgery.
15. Previous rectal surgery (other than hemorrhoidectomy) or known history of rectal disease.

Nephrology

16. Compromised renal function defined as serum creatinine > 2.0 mg/dl.
17. Hydronephrosis (Grade 2 or higher).

Oncology

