11.7 Retroperitoneal Ultrasound (Renal and Bladder)

A retroperitoneal ultrasound of the abdomen and pelvis will be performed to assess the patients' urinary tract integrity at pre-procedure baseline, 2 weeks (as applicable) and again at their 6 week follow-up appointment. These retroperitoneal ultrasound imaging studies will be used to determine the study's satisfaction of the primary safety endpoint, in particular the presence of permanent damage to the bladder, trigone, or ureteral orifices. The written request for sonographic examination will include sufficient information directing the examiner to allow for appropriate performance of the ultrasound focusing on the primary safety endpoint criteria listed above. Retroperitoneal ultrasound guidelines (urinary tract and bowel):

Kidney Assessment

- Kidney examination should include transverse and long-axis (sagittal or coronal) views
- Assessment of the cortices and renal pelvises should be made
- The maximum length of each kidney should be recorded
- For vascular kidney examination, Doppler ultrasound can be utilized to assess renal arterial and venous patency and suspected renal artery stenosis
- The kidneys and perirenal regions should be assessed for abnormalities
- Measurements should be taken of any abnormalities

Bladder Assessment

- For examination of the complete urinary tract, transverse and longitudinal (sagittal or coronal) images of the distended urinary bladder should be included if possible
- Abnormalities of the bladder wall or lumen should be noted

Bowel Assessment

- Evaluation of the bowel for wall thickening, dilatation, muscular hypertrophy, masses, vascularity, and other abnormalities can be made
- Identification of bowel perforations or fistulas should be reported

Any site reported abnormalities present on the 2 week (if abnormal BUN or Creatinine) or 6-week ultrasound that were not present at baseline will be reviewed as potential device-related serious complications and a final adjudication will be made by the Clinical Events Committee. The retroperitoneal ultrasound will be used in conjunction with TRUS to adjudicate the potential complications.

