12.1 Sample Size Justification

For the trial to be successful, the primary efficacy endpoint must be adequately powered.

For the primary efficacy endpoint to be met, the proportion of the ITT analysis population that responds to therapy must be statistically significantly greater than 50%. A responder is defined as a subject who has an IPSS improvement $\geq 30\%$ post-treatment, as compared to baseline.

The required sample size for this endpoint was calculated based on the following assumptions:

- One-sample exact binomial hypothesis test of proportions,
- Type I error of 0.025, one sided,
- Statistical power of 90%, and
- Population responder rate of at least 67.5%.

The responder rate in the Rezūm II trial was 77.9% (106/136). A population rate of at least 67.5% is selected as a conservative assumption for the responder rate in the Rezūm XL trial based on the lower bound of a two-sided 99% confidence interval for the responder rate in the Rezūm II trial. Based on these assumptions, a sample size of at least 88 intention-to-treat subjects is required for analysis.

Additional subjects may be screened since some subjects that consent may exit the study without being enrolled (e.g. due to withdrawal of consent or not meeting eligibility criteria).

12.2 Primary Safety Endpoint - Post Procedure Device Related Serious Complications:

This safety endpoint will be to demonstrate that the composite rate of post procedure device related serious complications at 6 months is acceptably low.

The following hypothesis will be tested in a one-sided exact binomial test at the 5% significance level.

$$H_0: P_{\text{Rezūm6}} \geq 12\%$$

$$H_1: P_{\text{Rezūm6}} < 12\%$$

Where:

$P_{\text{Rezūm6}}$ is the proportion of subjects experiencing one or more safety composite events within 6 months post-procedure. The safety endpoint is a composite of the four types of events listed below.

Device-related serious complications for this endpoint are defined as:

- Device perforation of the rectum or GI tract
- Device related formation of fistula between the rectum and urethra
- Permanent damage to the bladder, trigone or ureteral orifices requiring intervention
- Grade 2 hydronephrosis

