The adverse events listed above will be adjudicated by the clinical events committee (CEC) for this endpoint. With a sample size of 88 subjects, a performance goal of 12% requires that no more than 5 subjects (5.7%) experience a device-related serious complication in order for this endpoint to be met.

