12.6 Other Analyses

Adverse events, protocol deviations and device malfunction will be tabulated and included in the analysis. Descriptive statistics will be used in reporting these outcomes.

13 Definition of Study Success

The study will be declared a success if the primary efficacy and safety endpoints are met.

14 Definition of Adverse Event(s)

For purposes of this study, an AE is defined as any adverse change (i.e., *de novo* or preexisting condition) from the subject's baseline medical condition(s) occurring during the course of the study. For the purpose of AE documentation, the start of the study is defined as any time after the treatment has been initiated.

Subjects must be monitored from the start of the study, and throughout the duration of the study, for any and all AEs, including those observed as well as those reported by the subject. All AEs are to be documented by the investigator on the appropriate CRF. All AEs will remain under medical supervision until the Investigator deems the AE to be resolved, returned to baseline or stabilized at a new level no longer requiring medical supervision.

All AEs will be recorded in the CRF whether considered procedure-related or not, and will be classified as described in section 14.7.

Pre-existing conditions will not be reported as an AE unless there is an adverse change in that condition. Any AE which resolves and then recurs will be reported as a separate AE.

An AE may be volunteered spontaneously by the subject or discovered as a result of questioning or physical examination by an investigator or study staff.

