14.11 Independent Review of Retroperitoneal Ultrasound (renal and bladder)

An independent reviewer will review all baseline, 2 week (if applicable) and 6 week retroperitoneal ultrasounds to assess for any unreported device-related serious complications defined as:

- Device perforation of the rectum or GI tract

- Device related formation of fistula between the rectum and urethra
- Permanent damage to the bladder, trigone or ureteral orifices requiring intervention

If any of the above are noted, a request will be sent to the site to report such event. Copies of the retroperitoneal ultrasound will be available for the CEC if they deem necessary.

15 Training

The Sponsor will be responsible for training appropriate clinical site study personnel. All physicians proctored by the Sponsor, as well as other trained physicians, must have completed the commercial training program. To ensure proper procedural technique, uniform data collection and protocol compliance, the Sponsor will present a formal training session to personnel at each study site. At this training session the Sponsor will review the study protocol, techniques for the identification of eligible subjects, instructions on data collection, schedules for follow-up assessments, and regulatory requirements.

16 Data Management

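### Section 11.7 sends only scan findings absent at baseline to the CEC and does not mention worsening, so a Grade 1 to Grade 2 hydronephrosis progression may reach adjudication only through a site AE report

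*Combined protocol and SAP*

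**What the plan says.** - **Eligibility (section 9.4.2, exclusion 17).** The excluded condition is "Hydronephrosis (Grade 2 or higher"; Grade 1 is not excluded.
- **Endpoint (section 12.2).** "The safety endpoint is a composite of the four types of events listed below", and the fourth is "Grade 2 hydronephrosis". The window is 6 months. On adjudication: "The adverse events listed above will be adjudicated by the clinical events committee (CEC) for this endpoint".
- **Scan trigger (section 11.7).** Site-reported abnormalities on the 2-week scan (done only if BUN or creatinine is abnormal) or the "6-week ultrasound that were not present at baseline will be reviewed as potential device-related serious complications", with final adjudication by the CEC. For the kidneys the section adds "Measurements should be taken of any abnormalities". It does not mention a hydronephrosis grade or a comparison of grade with baseline.
- **Independent scan review (section 14.11).** A reader examines all baseline, 2-week and 6-week scans to "assess for any unreported device-related serious complications defined as" three types: perforation, fistula, and permanent damage to the bladder, trigone or ureteral orifices. Hydronephrosis is not among them.
- **AE rule (section 14).** "Pre-existing conditions will not be reported as an AE unless there is an adverse change in that condition". Sections 14.7 and 19.1 require every AE to be recorded and have the CEC adjudicate reported events possibly related to the device, procedure or disease.

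**The concern.** A man with Grade 1 hydronephrosis at entry needs only a one-grade change to reach the composite threshold. If the abnormality in section 11.7 is taken to be hydronephrosis as such, it was already present at baseline and the scan trigger does not fire when it worsens. His case then depends on the site recognising the change, which may be silent, and filing it as an AE.

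Table 10-2 schedules the retroperitoneal ultrasound at baseline, at 6 weeks and, conditionally, at 2 weeks. For most men there is thus one scheduled follow-up look at the kidneys. In a single-arm test against a 12% ceiling, any event that is not counted lowers the observed rate and favours a finding of safety.

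**Working it through.** **1. The plan's own figure.** Inputs from section 12.2: N = 88, performance goal 12%, one-sided exact binomial test at 5%, at most 5 subjects with an event.

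P(X ≤ c) = Σ (k = 0 to c) C(88, k) × 0.12^k × 0.88^(88−k)

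| Events c | c/88 | P(X ≤ c) at 12% | Result at 5% |
|---|---|---|---|
| 5 | 5.7% | 0.0393 | passes |
| 6 | 6.8% | 0.0846 | fails |

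The stated limit of 5 subjects (5.7%) is reproduced. If six men truly have an event and one is not counted, the recorded 5 of 88 passes.

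**2. The scan trigger applied to three records.** Two readings of the section 11.7 sentence are possible:

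| Baseline → week 6 | Abnormality means hydronephrosis of any grade | Abnormality means Grade 2 hydronephrosis |
|---|---|---|
| None → Grade 2 | triggers | triggers |
| Grade 1 → Grade 1 | does not trigger | does not trigger |
| Grade 1 → Grade 2 | does not trigger | triggers |

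The readings differ only in the third row, which is the row that matters for the endpoint. Nothing in section 11.7 chooses between them.

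**3. Other routes to the CEC for the third record.**
- *AE report:* open. Worsening of a pre-existing condition is an AE (section 14), goes on a CRF (14.7), and is adjudicated if possibly related (19.1). Section 12.2 has the CEC adjudicate all four components, with no condition that the finding be new. This route starts with the site.
- *Independent scan reader:* not provided for. Section 14.11 is meant to find what sites did not report, but its list has three of the four components in section 12.2 and omits hydronephrosis.

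**4. Size.** The number of missed events would depend on how many enrolled men have Grade 1, how many progress, how many progressions are judged device-related, and how many of those the site does not report. The documents give none of these, so no estimate is possible.

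**The case against.** The strongest reply is that the sentence already covers the case. The component is Grade 2 hydronephrosis, not hydronephrosis of any grade. Grade 2 or higher is barred at entry, so in an eligible man a Grade 2 finding is necessarily absent at baseline. The revision history shows that the exclusion and the Grade 2 threshold came in together in Rev 04, which suggests they were meant to match. This is a fair reading and may be the intended one. It stands as a reason to call the wording ambiguous rather than wrong. It does not remove the problem, because two sites could handle the same pair of scans differently.

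Second, the AE route exists and the CEC's remit in section 12.2 is not limited to new findings. That stands too. A narrower scan trigger beside a broader reporting duty is not a contradiction, since a site can follow both.

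Third, section 11.7 depends on site reporting in every case, including a man with no hydronephrosis at baseline, and it requires the scan request to point the examiner to the safety endpoint criteria. So the contrast between the two kinds of case is one of degree: in one the protocol tells the site explicitly that the finding goes to review, and in the other it may not.

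A reader might also infer a large rise in the false-pass risk. If 10%, 20% or 30% of all composite events went uncounted at a true rate of 12%, the chance of passing would go from 3.9% to 7.6%, 14.0% or 24.2%. The arithmetic is right, but the documents do not support the inputs. It assumes that share of events, over all four components, arises in men with Grade 1 at baseline, and that every one is lost despite the AE route. At 12%, 88 men give about 10.6 events (88 × 0.12). The 30% case therefore needs about three such progressions, each device-related and none reported.

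**Conclusion.** The point holds as a weakness in ascertainment. The section 11.7 trigger does not mention worsening, can be read to leave out a Grade 1 to Grade 2 progression, and is not backed up by section 14.11. Any resulting error favours passing.

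A reader might infer that such a man cannot reach the CEC or cannot count as an event. The documents do not say that: sections 12.2, 14, 14.7 and 19.1 leave the route open, provided the site reports the change.

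The effect cannot be sized. What is firm is the boundary, 5 of 88 passing (p = 0.039) and 6 of 88 failing (p = 0.085). That margin applies to any missed event of any component and is not evidence that one will be missed. The conclusion rests on the wording of section 11.7 and on Grade 1 being eligible. The CRFs are not in the documents, so whether they already capture the grade is unknown.

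**What to change.** 1. In section 11.7, extend the trigger to abnormalities *not present at baseline, or worsened since baseline (for hydronephrosis, any increase in grade)*.
2. Make sure the hydronephrosis grade is recorded, preferably for each kidney, at baseline and at every follow-up scan. If the CRF already does this, a cross-reference in section 11.7 is enough.
3. Add Grade 2 hydronephrosis to the list in section 14.11, so that the independent reader looks for all four components in section 12.2.

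The cost is two short text edits and perhaps one CRF field. The CEC may have a few more scans to review, and the observed safety rate may be slightly less favourable. Eligibility, treatment, sample size and the test itself are unchanged.

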11.8 Genitourinary Perforation and Assessment of Fistula Formation

A urine culture and an abdominal & pelvic exam will be conducted at the 2 and 6 week follow-up visit to assess for potential perforation of the rectum or GI tract; or fistula formation between the urethra and rectum.

The patients also will be asked the following questions:

- 1) Are you passing gas (air) in your urine? Checking for pneumaturia

- 2) Are you seeing any fresh blood in your stool or when you wipe? Checking for hematochezia
- 3) Are you seeing any urine coming from your rectum? Checking for recto-urethral fistulas

If a patient answers yes to any of the three questions, and the patient's urine culture is positive for infection, then the patient will undergo an intravenous rectal and oral contrast CT exam, or any other evaluation method deemed necessary if clinical suspicion exists, to rule out perforation of the GI or GU tracts and/or fistula formation.

12 Statistical Considerations

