10.5.3 Scheduled Follow-up Evaluations

The following evaluations will be completed at each visit as indicated in Table 10-2. For the subset of subjects who agree to endoscopic evaluations, an examination will be performed at their 6 month visit after all the questionnaires have been answered.

TABLE 10-2: SCHEDULE OF VISITS

	Baseline Pre-Op	Intra Procedure	Discharge	Cath Removal	2 weeks	6 weeks	3 months	6 months	12 months	Annually to 3 years	Unscheduled	
Compliance window				Min. 7 days post	± 2 days	± 7 days	± 7days	± 30 days	± 30 days	± 60 days		
Physical Exam	√			Voiding Trial and, if appropriate, Indwelling Catheter removal*	√	√	√	√	√	√		
Medical History	√											
Blood Analysis (CBC, BUN, Blood Sugar, Serum Creatinine)	√				√							
Urine Analysis (Sugar, Protein, WBC/RBC, Bacteria)	√	√			√	√						
Abdominal and Pelvic Exam					√	√						
Uroflow (Qmax + PVR)	√					√	√	√	√	√	√	
Urodynamics Assessment	√								√ (optional)			
IPSS (Standard)	√					√	√	√	√	√	√	
IPSS (Acute)					√							
Additional Questionnaires: • IIEF • MSHQ-EjD • BPHII • EQ-5D-5L	√						√	√	√	√	√	
PGI-I QoL							√	√	√	√	√	
Resumption to Activities questionnaire					√	√ ¹						
Subject satisfaction questionnaire									√	√	√	
Prostate specific antigen (PSA)	√							√	√	√	√	
Intravesical Protrusion (TAUS)	√							√	√	√		

	Baseline Pre-Op	Intra Procedure	Discharge	Cath Removal	2 weeks	6 weeks	3 months	6 months	12 months	Annually to 3 years	Unscheduled	
Prostate volume (TRUS)	√							√	√	√		
Retroperitoneal ultrasound (renal and bladder)	√				√ ³	√						
Digital Rectal Exam (DRE)	√						√	√	√	√		
Rezūm Procedure		√										
Subject pain scale	√		√			√	√	√	√			
Adverse event(s) review		√				√	√	√	√	√	√	√
Medication(s) used	√	√	√			√	√	√	√	√	√	√
Flexible Cystoscopy (recorded)	√ ²	√ ²							√ ²			
CT Scan (Intravenous rectal and oral contrast)						√ ⁴ If needed	√ ⁴ If needed					

¹If subjects have not resumed to activities by 2 weeks, a repeat of the Resume to Activities Questionnaire should be done at the 6 week follow-up

²Videos to be reviewed by CEC to assess integrity to the bladder, trigone, or ureteral orifices

³Only required if subject's BUN and/or Creatinine level is abnormal from their baseline assessment

⁴Only required if subject answers "yes" to abnormalities in the abdominal and pelvic exam questions AND they have a positive infection identified from the urine culture then a CT Scan, or other exams deemed necessary are to be ordered.

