14.8 Relationship of AEs to the Rezūm Device

A description of how an AE relates to the study procedure will be reported on the Adverse Event CRF and be determined by the Investigator using the following definitions:

- **Definite:** The AE follows a reasonable temporal sequence from the time of the index procedure, which includes AEs that occur during the index procedure or during the follow-up period.
- **Probable:** The AE follows a reasonable temporal sequence from the time of the index procedure, and the possibility can be excluded that factors other than the index procedure, such as underlying disease, concomitant drugs, or concurrent treatment caused the AE.
- **Possible:** The AE follows a reasonable temporal sequence from the time of the index procedure and the possibility of index procedure involvement cannot be excluded. However, other factors such as underlying disease, concomitant medications, or concurrent treatment are presumable.
- **Unlikely:** The AE has an improbable temporal sequence from the time of the index procedure, or such AE can be reasonably explained by other factors, including underlying disease, concomitant medication, or concurrent treatment.
- **Not related:** The AE has no temporal sequence from the time of the index procedure, or it can be explained by other factors, including underlying disease, concomitant medication, or concurrent treatment.

Those SAEs that are possibly related to the device, the procedure, or the disease state being treated will be reviewed and adjudicated by the CEC. The CEC will review in tabular format all non-device/procedure/disease-related SAEs.

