19.1 Clinical Events Committee (CEC)

Evaluation and adjudication of safety data (e.g., SAEs, all deaths, etc.) will be performed on an ongoing basis by the CEC. This CEC will be comprised of three independent physician reviewers with an expertise in urology. Members of the CEC will not be participants in the study.

All reported adverse events that are possibly related to the device, the procedure, or disease state being treated will be reviewed and adjudicated by the CEC. The CEC will review in tabular format all non-device/procedure/disease-related events.

20 Study Contact

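### Table 10-2 footnote 4 ties all perforation and fistula work-up to a positive urine culture, and Section 11.8 has no rule sending a yes answer to the Clinical Events Committee

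*Combined protocol and SAP*

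**What the plan says.** Section 11.8 schedules a urine culture, an abdominal and pelvic exam and three questions (air in the urine, fresh blood in the stool or on wiping, urine from the rectum) at 2 and 6 weeks. After a yes to any question, a second condition applies: "urine culture is positive for infection, then the patient will undergo an intravenous rectal and oral contrast CT exam". The sentence continues "or any other evaluation method deemed necessary if clinical suspicion exists".

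Table 10-2 footnote 4 (Section 10.5.3) states the same rule for sites working from the visit schedule. It requires abnormal answers, joined by a capitalised AND to a second condition: "they have a positive infection identified from the urine culture then a CT Scan, or other exams deemed necessary are to be ordered". It does not mention clinical suspicion.

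Section 11.7 treats ultrasound differently. New site-reported abnormalities "not present at baseline will be reviewed as potential device-related serious complications and a final adjudication will be made by the Clinical Events Committee". Section 11.8 does not mention the CEC.

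The general adverse event route is in three places:
- Section 14: "All AEs will be recorded in the CRF whether considered procedure-related or not". This includes events "discovered as a result of questioning or physical examination by an investigator or study staff".
- Section 14.8: the relationship of an event to the procedure "will be reported on the Adverse Event CRF and be determined by the Investigator using the following definitions".
- Section 19.1, on the CEC's work: "All reported adverse events that are possibly related to the device, the procedure, or disease state being treated will be reviewed and adjudicated". Events judged unrelated are reviewed only in tabular form.

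**The concern.** The three questions are the only scheduled direct symptom screen for fistula. A man who reports urine from the rectum but has a negative culture has no mandatory work-up. A site that follows footnote 4 literally could conclude that even discretionary exams wait on the culture, which is narrower than Section 11.8 appears to intend.

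The answer also has no assured route to the body that decides the endpoint. It is individually adjudicated only if the site records it as an adverse event and judges it possibly related. Fresh blood on wiping is easily put down to another cause.

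Patient safety is one stake. The other is ascertainment: in a single-arm test against a 12% goal, a missed event can only favour success.

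**Working it through.** **1. The plan's own limit.** Inputs from Section 12.2: n = 88, goal 12%, one-sided exact binomial test at 5%.
- P(X ≤ 5 | 88, 0.12) = 0.0393, which is below 0.05 and passes.
- P(X ≤ 6 | 88, 0.12) = 0.0846, which is above 0.05 and fails.

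The stated limit of 5 subjects (5.7%) is reproduced.

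**2. When a miss changes the verdict.** Let T be the true number of subjects with a composite event and m the number missed. The verdict changes only if T ≥ 6 and T − m ≤ 5. With m = 1, T must be exactly 6. With m = 2, T must be 6 or 7 (7/88 gives p = 0.157).

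**3. How likely T = 6 is.** P(T = 6) = C(88,6) p^6 (1 − p)^82. The documents give no composite rate for this population, so p is assumed over a range.

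| Assumed true rate p | P(T = 6) |
|---|---|
| 1.5% | 0.2% |
| 2% | 0.7% |
| 4% | 7.8% |
| 6% | 15.8% |
| 6.8% (6/88, the maximum) | 16.6% |
| 8% | 15.2% |
| 10% | 9.6% |
| 12% | 4.5% |

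The 1.5% row uses 2/136, the proportion with any related serious event at 0–3 months in Rezūm II (Table 8-9). None of those events was of a composite type, and the prostates were smaller, so it is only a guide.

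These are ceilings for a single miss. The missed event must also be a perforation or fistula, two of the four components, and must escape every other route to detection.

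**4. Tracing a yes answer.**

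| Culture | Section 11.8 | Footnote 4 | Route to the CEC |
|---|---|---|---|
| Positive | CT, or other evaluation as judged necessary | CT or other exams ordered | General adverse event route |
| Negative | No mandatory CT; other evaluation on suspicion, scope ambiguous | Nothing required; other exams share the AND | General adverse event route |

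Neither row contains a direct CEC rule like the one in Section 11.7.

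**5. Timing of the culture.** Section 10.5.1 places catheter removal at days 7–10 and requires antibiotics for 3 days afterwards, so to days 10–13. The 2-week visit, ± 2 days, falls on days 12–16. The periods overlap directly only when removal is on day 9 or 10 and the visit is on day 12 or 13. A culture suppressed by treatment is possible, but this is an inference from the schedule. The culture is repeated at 6 weeks.

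**The case against.** The strongest reply is that the plan handles this centrally and Section 11.8 need not repeat it. Much of that stands.
- All adverse events are recorded, including those found by questioning. The bar for a possible relationship is low: procedure involvement need only be impossible to exclude. New pneumaturia or urine from the rectum soon after transurethral steam would hardly be called unrelated. The CEC, not the site, decides what is serious (Section 14.5).
- Every subject has a 6-week retroperitoneal ultrasound, whose guidelines ask for bowel perforations or fistulas to be reported. An independent reader looks for unreported events (Section 14.11).
- Recorded cystoscopy follows the procedure and is repeated at 6 months. Section 11.4 states this for all; Section 10.5.3 limits the 6-month examination to those who agree. Rectal examination continues at 3 and 6 months, though for another stated purpose.
- Section 11.7 routes imaging findings, whereas Section 11.8 collects symptoms, one of them non-specific. Handling them differently is defensible.
- Section 7.1 reports no perforation in trials or commercial use.

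These points make a miss unlikely. They do not remove the mismatch between footnote 4 and Section 11.8, or the dependence on the investigator's relatedness call. The non-specific nature of rectal bleeding justifies a filter on that question, but not on the other two.

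A reader might infer that the plan forbids work-up when the culture is negative. It does not: footnote 4 says when exams are required, Section 11.8 has its suspicion clause, and the Revision 04 log says the added language was meant to allow other evaluations.

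**Conclusion.** This is a minor point about wording and routing, held with medium confidence. Footnote 4 is narrower than Section 11.8, and Section 11.8 lacks the CEC rule found in Section 11.7. The 5/88 limit is correct and unaffected.

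The number of missed events cannot be derived from the documents. The chance that one miss would decide the verdict is at most 16.6% under any assumed rate, and far lower once the other routes are counted.

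Three stronger readings are not supported:
- That a yes with a negative culture never reaches the CEC. It does if recorded and judged possibly related, and otherwise it appears in tabular review.
- That the safety test's error rate is seriously inflated. At a true composite rate of 12%, the chance of a false pass would rise from 3.9% to 34.6% if 75% of events were perforation or fistula and half of those were missed. That means 0.12 × 0.75 = 9% of subjects with such an injury, which nothing in the documents supports.
- That the culture condition on mandatory CT is itself an error. It is a design choice and can stay, provided that suspicion alone can prompt other evaluation.

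**What to change.** (a) Reword Section 11.8 and Table 10-2 footnote 4 identically, so that other evaluation on clinical suspicion applies whatever the culture result. Leave the mandatory CT trigger unchanged.

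(b) Add to Section 11.8 that the following go to the CEC as potential composite events, whatever the culture result or the investigator's view of relatedness: every yes on pneumaturia or urine from the rectum, and every yes on fresh blood that is new or worse than before the procedure. Including worse matters, because a filter on new symptoms alone would drop a man with earlier bleeding who then has an injury.

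The questions are asked only at 2 and 6 weeks, so the site should record at that visit whether the bleeding was present before the procedure and whether it has worsened.

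The cost is protocol wording, one CRF item and a few more non-specific records for the CEC. Exclusion 15 permits prior hemorrhoidectomy, so some reports of blood will have a benign explanation; the comparison with the pre-procedure state limits these. No mandatory test is added.
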